5.5 Exposure to Study Medication and Treatment Compliance

Number of subjects receiving study medication will be summarized per nebulization and day by treatment group. Per each nebulization the following information will be summarized:

- Administration fully done (yes/no)
- Inhalation period interrupted (yes/no)
- Contact with face mask:

- Close contact with the face (and mouth and nose covered) most of the time (>75%)
- Close contact with the face (and mouth and nose covered) approx. half of the time (25%-75%)
- Close contact almost not achieved (<25% of the time)
- Problem occurrence during use of the device (yes/no)
- Device issue resulted in an adverse event (yes/no)

A listing by subject will also be produced.

6 SAFETY

Safety evaluation will take into account the recorded AEs, vital signs, laboratory assessments, physical examination findings, respiratory distress assessment, hospitalization and any other parameter that is relevant for safety assessment. All safety analyses will be based on the safety population.

6.1 Adverse Events

AEs will be coded by SOC and PT using the latest version of MedDRA available at the time of database lock. All adverse events recorded during the study will be listed with treatment emergent AEs flagged.

If an adverse event start date is missing or unknown, the adverse event will be considered as emergent (unless the adverse event end date is before the first dose of study drug).

When start and/or end dates of an adverse event are only partially known, adverse events will be categorized using the following rules:

- If the end time is missing and the end date is before (<) the first dose of study drug, then the adverse event will not be considered as emergent.
- If the partial end date is before (<) the first dose of study drug (i.e., year or year & month is/are before the first dose of study drug year or year & month), then the adverse event will not be considered as emergent.
- If the start time is missing and the start date is equal or after (≥) the first dose of study drug, then the adverse event will be considered as emergent.
- If the partial start date is equal or after (≥) the first dose of study drug (ie, year or year & month is/are after or the same as the first dose of study drug year or year & month), then the adverse event will be considered as emergent.

No imputation will be done of missing/partial date(time) fields. The dates and times will be presented in the listings as captured in the eCRF.

TEAEs or treatment-emergent SAEs are events temporally associated with the use of study drug (occurring during or after the first dose of study drug, or worsening in severity (for pre-existing conditions)), whether considered related to the study drug or not.

In the TEAE overview table, number and percentage of subjects for the following items will be provided:

- Subjects with at least one treatment-emergent adverse event (TEAE)
- Subjects with at least one serious TEAE
- Subjects with at least one TEAE leading to death
- Subjects with at least one severe TEAE as classified by the investigator
- Subjects with at least one TEAE for which the study drug was interrupted
- Subjects with at least one TEAE for which the study drug was discontinued
- Subjects with at least one TEAE that was considered treatment-related (relationship to study drug is related or possibly related or missing) by the investigator.
- Subjects with at least one serious TEAE that was considered treatment-related (relationship to study drug is related or possibly related or missing) by the investigator.

The incidence (number and percentage) of TEAEs will be summarized by SOC/PT, severity (mild, moderate, severe, missing) and relationship to study drug (related, possibly related, unlikely related, not related, not applicable, missing) for each treatment group.

Each AE listing will include;

- Subject number/ site
- Start and stop date/time of each nebulization
- AE description
- AE system organ class
- AE preferred term (flagging serious TEAEs with an asterisk *)
- TEAE indicator flag
- AE start and end date/time
- AE onset day
- AE duration
- AE seriousness
- AE severity
- AE drug relatedness
- AE relatedness to study procedure
- AE outcome
- AE action taken
- Concomitant therapy started (yes/no)

The following counting rules for TEAEs will be used:

A subject experiencing AEs with the same SOC or PT more than once after dosing will be counted as following;

- For tables counting TEAEs by intensity, only the most severe TEAE will be counted for each subject within the corresponding SOC/PT.
- For tables counting TEAEs by relationship, only the most related TEAE will be counted for each subject within the corresponding SOC/PT.

The denominator for the percentages will be the number of subjects in the safety population for each treatment group.

6.2 Adverse events leading to study drug discontinuation

TEAEs leading to discontinuation from the study drug will be listed for each subject and summarized by SOC/PT for each treatment group.

6.3 Serious adverse events

Serious TEAEs will be summarized by SOC/PT for each treatment group.

SAEs will be listed by subject.

6.4 Non-Serious adverse events

Non-Serious TEAEs will be summarized by SOC/PT for each treatment group.

6.5 Laboratory Evaluations

Blood sampling for laboratory clinical chemistry and hematology will be obtained at screening and at Follow Up and results will be presented in standard international (SI) units.

The following parameters will be measured:

- Hematology: hemoglobin, hematocrit, red blood cell count and indices, mean corpuscular hemoglobin, mean corpuscular hemoglobin concentration, platelet count (or estimate), white blood cell count including differential (lymphocytes, neutrophils, monocytes, basophils, eosinophils).
- Clinical chemistry: alanine aminotransferase, aspartate aminotransferase, creatinine, sodium, potassium, chloride, C-reactive protein, γ -glutamyl-transferase, blood urea nitrogen.

A listing for results outside the reference ranges or clinical significance will be produced and will include the result, date and time of measurement, change from Baseline, reference range and flags for measurements that are outside the reference range (where applicable). Abnormal values will be flagged as "L" (for values lower than the lower limit of the reference range) and "H" (for values higher than the upper limit of the reference range). Clinical significance(abnormality) will be indicated as abnormal, "CS" (clinically significant) or abnormal, "NCS" (not clinically significant). The listing will present all laboratory data for subjects with an out-of-range or clinical significant result.

Summary tabulations (absolute and change from baseline values) of hematology and clinical chemistry laboratory tests will be presented by treatment group and time point.

Additional tabulations will present the shift in abnormality (L/N/H/L+H) at the worst post-baseline time point, including unscheduled measurements, versus the baseline abnormality (L/N/H). Only parameters with a given normal range will be presented.

Any safety laboratory values given as '<xx' or '>xx' in the database will be imputed with the absolute value of the number without the sign (e.g., <2.2 will be imputed as 2.2) for the calculation descriptive statistics. Orginal value '<xx' where xx equals the lower limit of the normal range will be classified as abnormaly low. Orginal value '>xx' where xx equals the

upper limit of the normal range will be classified as abnormal high. In the listings, no imputations will be performed and all data will be displayed as recorded in the database.

6.6 Physical Examination

A physical examination including heart auscultation, examination of abdomen, skin, ears/nose/throat will be performed as described in the schedule of assessments as outlined in the CSP (section 3.6.3.6). For each body system, any abnormalities will be documented.

All reported abnormalities with the assessment of Clinical Significance in the physical examination will be listed by subject and time point for each body system.

6.7 Vital Signs and Respiratory Distress Assessment (RDA)

Summary tabulations (absolute values and changes from baseline (if applicable)) for vital signs (temperature (°C), weight (kg), heart rate (HR) (bpm), blood oxygen (Sp02) level (%), and respiratory rate (breaths/min)) will be presented by treatment group and time point. Measurements obtained at baseline and post-baseline will be included in the tabulations for the treatment received.

Hear Rate collection method, SpO2 measurement location, oxygen flow delivery (yes/no), duration of oxygen supplementation (hours) and RDA tests (lung auscultation (wheezing, lung fields affected by wheezing, crackles/crepitations), respiratory muscle retractions (supraclavicular, intercostal, subcostal), daytime coughing and night-time coughing) will be tabulated by treatment group and time point. Measurements obtained at baseline and post-baseline will be included in the tabulations for the treatment received.

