4.2 General Methods

All original and derived parameters as well as population characteristics will be listed and described using summary statistics. Frequency counts (number of subjects [n] and percentages) will be made for each qualitative variable. Descriptive statistics (n, mean, standard deviation [SD], median, minimum and maximum) will be calculated for each quantitative variable, and will only be presented if $n \geq 2$. If $n=1$, then only n and the mean will be displayed.

Repeated and unscheduled measurements will not be used for statistical analysis or summary tables, unless the repeated measurement was performed due to unreliable values/technical reasons, or the repeated measurement occurred prior to first study drug administration and is defined as the 'baseline'. The following rules will apply to any repeated measurements:

- If the repeated measurement occurs prior to the first study drug administration then the last obtained value of any repeated measurement will be used in the descriptive statistics.
- If the repeated measurement occurs after the first study drug administration then the original value of any repeated measurements will be used in the descriptive statistics.

All listings will include repeated and unscheduled measurements

All descriptive statistics will be presented by treatment group, and overall for disposition, demographic and baseline disease characteristics. The treatment groups were planned to be shown in the following order:

1. Placebo
2. Dose 1: target dose of 1.5 mg/kg

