4.3 Baseline Definition

The Baseline value is defined as the value observed at the last timepoint before first study drug administration.

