9 CHANGE FROM ANALYSIS PLANNED IN PROTOCOL

This section describes all changes from planned analyses in the protocol, after the protocol approval, but before the lock of the database, which did not lead to a protocol amendment.

1. Due to early termination of the trial, an abbreviated CSR will be produced instead of a full CSR and only a subset of all the statistical analyses that were planned in the protocol will be performed. . Following analyses have been excluded:
 - a. Evaluation of Antiviral effect: A listing showing the viral load data for Plaque assay and Rt-qPCR over time will be produced. Any other statistical analyses planned in the protocol, e.g. time-to-below the limit of quantification (BQL), time-to-undetectability, time-weighted average change from baseline up to Day 3 and Day 14, number and percent of subjects with undetectable RSV (from Day 1 to Day 14), number and percent of subjects with BQL and change from baseline in viral load, will not be performed
 - b. Evaluation of clinical activity:
 - i. No statistical analysis will be done on RDAI score, RACS and Global Severity Score (GSS)
 - ii. No statistical analyses will be included in the CSR on Clinical response, Adequate feeding , adequate oxygen supply
 - c. Correlation of immunogenicity: a listing of immunogenicity data (ADA and NAb) (as mentioned above in Section 8) will be produced. Statistical analysis for potential correlation between pre-Ab, TE ADA or NAb on safety, PK and efficacy, will not be performed. No descriptive summary statistics will be generated. There will also be no tabulation of prevalence of pre-Ab and incidence of ADA.
 - d. Evaluation of PD: The PD characteristics will not be reported in the abbreviated CSR (as serum levels of KL-6 will not be measured) and therefore no outputs will be produced
 - e. Parent(s)/Caregiver(s) assessment: No analysis will be done

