10.2 Computation of Derived Data

The following calculations and derivations will be used:

- Change from baseline of parameter: (visit value of parameter – baseline value of parameter)
 - If either the baseline or post-baseline value is missing, the change from baseline is set to missing.
- Duration of AE (days) = (end date - start date +1)

- If either the end or start date is incomplete or missing, the duration of AE is set to missing.
- If AE ongoing at the end of the trial then AE duration = trial termination date – AE start date + 1. In the listing the duration will be presented as ‘>x days’ rather than ‘x days’.
- Hospitalization or ICU duration (days) = discharge date/time – admision date/time
 - If either the end or start time is missing, the duration is calculated using the date part only then; duration = discharge date – admission date +1.
 - If the subject is still hospitalized or in ICU at the end of the trial then the duration = trial termination date – admission date +1
- Time since onset RSV signs and symptoms (days) = date of ICF – start date of symptom + 1.
- AE onset day = AE start date - first study drug administration date + 1 (when AE start date \geq first study drug administration date
 - If AE start date < first study drug administration date then; AE onset day = AE start date - first study drug administration date
- Duration of oxygen supplementation (hours) is defined as total time of reported oxygen supply according to oxygen supplementation form.
 - If the time is missing or the date is incomplete then the duration is set to missing.

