Table 14.3.3.1: Vital signs: Descriptive statistics of the actual values and changes from baseline per time point (Safety Population)

Test: Vital sign parameter (unit)

Treatment Group	Scheduled day/ time	Result						Change from baseline					
		n	Mean	SD	Median	Min	Max	n	Mean	SD	Median	Min	Max
Xxxxxx	Baseline	X	XX	XX	XX	XX	XXX						
	Day x	X	XX	XX	XX	XX	XXX	X	XX	XX	XX	XX	XX
	...	X	XX	XX	XX	XX	XXX	X	XX	XX	XX	XX	XX
	Follow-up	X	XX	XX	XX	XX	XXX	X	XX	XX	XX	XX	XX
...	...	X	XX	XX	XX	XX	XXX						

Max = maximum; Min: minimum; SD: standard deviation.

Baseline is defined as the last observation prior to first study drug administration.

Note to Programmer: Each parameter on a new page; Table sorted first by treatment group and then by time point.

Please display the following variables; temperature (°C), weight (kg), heart rate (HR) (bpm), blood oxygen (SpO2) level (%), and duration of oxygen supplementation (hours)

Please display duration of oxygen supplementation (hours) at the end (the lastest test) and erase Schedule day/time and change from baseline columns as not needed.

Table 14.3.3.2: Vital signs: Tabulations per time point (Safety Population)

Test: XXXXXX

Time Point	Category	Statistic	Placebo	ALX-0171 1.5 mg	Observed Value
			(N = XX)	(N = XX)	
(Baseline)	XXX	n (%)	XX (XX.XX)	XX (XX.XX)	
	XXX	n (%)	XX (XX.XX)	XX (XX.XX)	
	----	n (%)	XX (XX.XX)	XX (XX.XX)	
XXXXXX	XXX	n (%)	XX (XX.XX)	XX (XX.XX)	
	XXX	n (%)	XX (XX.XX)	XX (XX.XX)	
	----	n (%)	XX (XX.XX)	XX (XX.XX)	
XXXXXX	XXX	n (%)	XX (XX.XX)	XX (XX.XX)	
	XXX	n (%)	XX (XX.XX)	XX (XX.XX)	

N: number of subjects in the safety population; n: The number of subjects in the specific category; %: calculated using the number of subjects with non missing data in the safety population for the applicable treatment group as the denominator (n/(N non missing)*100).
 Baseline is defined as the last observation prior to first study drug administration.

Note to Programmer: Each parameter on a new page; Table sorted first by test, then by time point.
 Please display the following variables; Hear Rate collection method, Location of Sp02 measurement, Oxygen flow delivered (yes/no)

Table 14.3.4.1: RDA: Descriptive statistics of the actual values and changes from baseline in respiratory rate per time point (Safety Population)

Test: XXXXXX

Treatment Group	Scheduled day/ time	Result						Change from baseline					
		n	Mean	SD	Median	Min	Max	n	Mean	SD	Median	Min	Max
XXXXX	Baseline	X	XX	XX	XX	XX	XXX						

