15.2 Mock Listings

Listing 16.2.1.1: Subject Disposition (All screened subjects)

Subject Number/Site	Date of ICF	Randomization group	Date of Randomization	Randomization number	Treatment actually received*	Analysis population Safety
XXX/X		Placebo			Placebo	<YES>

All discrepancies between randomization and treatment group will be flagged.

Note to Programmer: Table sorted first by randomization group and then by subject ID.

Listing 16.2.1.2: Demographics (Safety Population)

Treatment Group: XXXXXX

Subject Number/ Site	Date of Randomiza- tion	Date of Gestational Age (weeks)	Age (month)	Gender	Ethnic Origin	Race	Asian	Height (cm)	Weight (kg)	Weight Category (kg)	Atopy History	Exposure to Tobacco	Exposure to Pets	Breast fed
XXX/X		XX	XX	MALE	HISPANIC OR LATINO	WHIT	E							
XXX/X		XX	XX	FEMALE	HISPANIC OR LATINO	ASIA	N	XXXXX						

Note to Programmer: Table sorted first by treatment group and then by subject number

Listing 16.2.1.3: Baseline Characteristics (Safety Population)

Treatment Group: XXXXXX

RSV Severity Criteria							
Subject Number/Site	Heart Rate (bpm) at Baseline	Blood Oxygen (SpO2) at Baseline	Time since onset	RSV Signs and Symptoms	Inadequate Oral Feeding (days)	Inadequate Oxygen Saturation	Inadequate Respiratory Distress

Note to Programmer: Table sorted first by treatment group and then by subject number

Listing 16.2.1.4: Medical History and Concomitant Diseases (Safety Population)

Treatment Group: XXXXXX

Subject Number/Site	Body System	Description of Disease/Procedure	Start Date DDMMYYYY	End Date DDMMYYYY	Ongoing at screening <YES>
<hr/>					

Note to Programmer: Table sorted first by treatment group and then by subject number

Listing 16.2.1.5: Prior and Concomitant Therapies (Safety Population)

Treatment Group: XXXXXX

Subject ID	ATC Level 4 Class verbatim	Prior/ Concomi- tant Preferred Term	First study drug administration Date/Time	Start Date/Time	End Date/Time	Ongoing at the end of trial?	Reason for use	Indication	Dose (unit)	Dosing frequency
				YYYY-MM-DD /HH:MM	YYYY-MM-DD /HH:MM	<YES>				

Prior medications are medications that were given prior to date/time of informed consent and which ended before date of informed consent
 Concomitant medications/oxygen supplementation therapies are medications/oxygen supplementation therapies which are ongoing at signing of informed consent or which started after the signing of informed consent

Listing 16.2.1.6: Exposure to Study Medication (Safety Population)

Treatment group : xxxx

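### SpO2 means and changes from baseline can mix readings on oxygen with readings on room air, and no planned output shows a post-baseline SpO2 value with the oxygen given at that reading.

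*SAP*

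**What the plan says.** SAP 6.7 plans summaries of absolute values and changes from baseline for the vital signs, in which "blood oxygen (Sp02) level (%), and respiratory rate (breaths/min)) will be presented by treatment group and time point". The programmer's note to mock Table 14.3.3.1 names the contents: "Please display the following variables; temperature (°C), weight (kg), heart rate (HR) (bpm), blood oxygen (SpO2) level (%), and duration of oxygen supplementation (hours". Neither place conditions SpO2 on oxygen status. The baseline rule in SAP 4.3 does not either: "The Baseline value is defined as the value observed at the last timepoint before first study drug administration".

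Oxygen appears in two other forms. Mock Table 14.3.3.2 gives a count per time point: "Please display the following variables; Hear Rate collection method, Location of Sp02 measurement, Oxygen flow delivered (yes/no". Duration is a single total per child under SAP 10.2: "Duration of oxygen supplementation (hours) is defined as total time of reported oxygen supply". The note to Table 14.3.3.1 removes the time-point and change columns for it.

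On listings, SAP 4.2 is general: "All original and derived parameters as well as population characteristics will be listed and described using summary statistics". The listing index (SAP 14) and the shells (SAP 15.2) nevertheless contain no vital-signs listing. The only SpO2 column in any listing is "Blood Oxygen (SpO2) at Baseline", in Listing 16.2.1.3.

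SAP 9 drops the protocol's analysis that used room-air saturation: "No statistical analyses will be included in the CSR on Clinical response, Adequate feeding , adequate oxygen supply".

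**The concern.** A saturation reading means little without knowing what oxygen the child was receiving. The protocol treats it that way. Inclusion criterion 8 (Protocol 3.2.1) uses a room-air value below 95%, or a documented value below 95% before supplementation. Clinical Response (Protocol 5.7) uses at least 95% on room air. The SAP's mean and mean change carry no such condition.

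SpO2 is named both as a safety outcome (SAP 3.3.1) and as a clinical activity outcome (SAP 3.3.2). SAP 6 counts vital signs in the safety evaluation, next to adverse events, respiratory distress and hospitalization. A fall in mean SpO2 could reflect successful weaning, and a rise could reflect the start of oxygen. With a purely descriptive report on 15 children, the tables and listings are the whole product, so a table that cannot be read correctly has no test or model behind it to compensate.

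**Working it through.** The plan states no power, effect size or event count on this point, so there is no figure to reproduce. The check compares what is collected with what is displayed, and then illustrates the effect with assumed readings.

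**1. Can oxygen status differ between baseline and a later reading?** Yes. Criterion 8 admits children on room air or on oxygen. Protocol 3.6.1.4 has removal of oxygen attempted at least three times a day when saturation is stable. SAP 4.3 takes the last pre-dose value whatever the oxygen status.

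**2. Does any planned output pair a post-baseline SpO2 value with oxygen status?**

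| Output | Shows | Pairs the two? |
|---|---|---|
| Table 14.3.3.1 | SpO2 value and change by arm and time point | No |
| Table 14.3.3.2 | Oxygen yes/no by time point | No, separate count |
| Oxygen duration (SAP 10.2) | One total per child | No |
| Listing 16.2.1.3 | Baseline SpO2 | Baseline only, no oxygen column |
| Listing 16.2.1.5 | Oxygen start and end times, dose column | No SpO2 |
| Listing 16.2.4.3 | Ventilation start, end and type | No SpO2 |
| AE and SAE outputs | Events | No SpO2 column |

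**3. Is information lost?** Take two assumed three-child arms at one time point.

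- Arm A: 97 on oxygen, 96 on room air, 92 on room air.
- Arm B: 97 on room air, 96 on room air, 92 on oxygen.

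In both, mean = (97 + 96 + 92)/3 = 95.0; SD = √[(2² + 1² + 3²)/2] = √7 = 2.65; median 96, minimum 92, maximum 97; oxygen yes 1/3. The planned summaries of the level and of oxygen use are identical. A combined variable (on oxygen / room air below 95% / room air 95% or above) gives 1/1/1 for A and 1/0/2 for B.

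**4. Can the change score point the wrong way?** Again with assumed readings:

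- Weaned, 97 on oxygen to 95 on room air: 95 - 97 = -2.
- Oxygen started, 94 on room air to 97 on oxygen: 97 - 94 = +3.

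Weaning does not fix the sign. With whole-percent readings of 95 to 100 at both times, the change runs from 95 - 100 = -5 to 100 - 95 = +5.

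**5. What does one such child add to an arm's mean change?** The contribution is d/n. The SAP gives 15 randomized but not the actual split, so the planned 12 active and 3 placebo (SAP 3.1) is assumed.

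| d | n = 12 | n = 3 |
|---|---|---|
| -2 | -2/12 = -0.17 | -2/3 = -0.67 |
| +3 | +3/12 = +0.25 | +3/3 = +1.00 |

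**The case against.** The strongest reply is proportion. The SAP serves an abbreviated report after development in infants was halted, nothing is tested, output was cut on purpose, and the size of the effect is unknown. All of that is true. It limits the point to descriptive safety reading, but it does not make the table readable.

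The missing listing can also be called a clerical mismatch between SAP 4.2 and the index, shared by every vital sign. That is fair. SpO2 is singled out because it is the one the protocol judges on room air, and a listing of SpO2 alone leaves SAP 4.2 unmet for the other vital signs.

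Clinical Response was a time-to-event composite with feeding, so dropping it did not cause the mixing. That is correct; dropping it only removed the planned analysis based on room-air saturation.

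Other outputs remain useful: time to discharge (discharge requires the response criteria), oxygen start and end times, ventilation, AEs for significant oximetry changes (Protocol 3.6.3.2) and the SAE triggers (Protocol 4.1.1). After discharge most readings should be on room air, so mixing within the mean level is mainly an in-hospital matter; changes from an on-oxygen baseline can still mix later. None of these outputs supplies the missing pairing.

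Two criticisms of the remedy stand in part. A footnote discloses the mixing without removing it. A single on-oxygen category also hides escalation from cannula to high flow, which only the listing would show.

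**Conclusion.** The concern holds. Programmed exactly as written, the SpO2 means and changes can mix oxygen and room-air readings, and no planned output lets a reader separate them after baseline. The absence of any post-baseline SpO2 listing also conflicts with SAP 4.2, and SAP 9 does not record it as a change.

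The size and direction in the actual data cannot be stated: the documents give no SpO2 values and no share of children on oxygen. The readings used above are illustrations, not bounds, and the per-child contributions rest on the planned 12:3 split. The consequence is confined to descriptive interpretation of safety and clinical activity. The sponsor should make the change, because it is cheap and the variable is a named outcome.

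**What to change.** - **Listing.** Add a by-subject listing of SpO2 with oxygen flow and method at each time point. This meets SAP 4.2 for SpO2 and reports the oxygen level and method that SAP 3.3.3 keeps as outcomes.
- **Combined variable.** Add to Table 14.3.3.2, per time point: on oxygen, room air below 95%, room air 95% or above. The cut is the protocol's own. A child with no recorded oxygen status goes in the missing row already required by SAP 12.6 and 12.7. State how a child on high-flow oxygen or ventilation is counted. Label the variable as a single reading, not the 4-hour Clinical Response criterion.
- **Footnote.** State under Table 14.3.3.1 that SpO2 means and changes are not adjusted for oxygen status and are to be read with the two outputs above.

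Splitting the means by oxygen status or by transition is not proposed; the groups would be too small.

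The cost is one listing, one tabulated variable and one footnote. Protocol 3.6.3.2 has oxygen flow and method captured in the eCRF together with SpO2, so no new data are needed. If the combined variable is derived in an ADaM dataset, SAP 4.5 requires double programming. The downside is sparse counts: 3 categories × 2 arms = 6 cells per time point for 15 children, with only 3 placebo children planned.

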13. APPENDICES

13.1. APPENDIX 1: RDAI AND RACS

The Respiratory Distress Assessment Instrument (RDAI) score is a 17-point score based on wheezing and retraction.

Variable	Number of Points						
	0	1	2	3	4	Max Points	
Wheezing							
Expiration	None	End	1-2	3-4	All	4	
Inspiration	None	Part	All	NA	NA	2	
Location	None	Segmental, ≤2-4 lung fields	Diffuse, ≥3-4 lung fields	NA	NA	2	
Retractions							
Supraclavicular	None	Mild	Moderate	Marked	NA	3	
Intercostal	None	Mild	Moderate	Marked	NA	3	
Subcostal	None	Mild	Moderate	Marked	NA	3	

NA=not applicable

The RDAI score is the sum of the row scores, with total range 0 to 17; higher scores indicate more severe disease.

The Respiratory Assessment Change Score (RACS) is the sum of the change in the RDAI score and a standardized score for the change in respiratory rate. The change in respiratory rate is assigned 1 point per each 10% change in the respiratory rate.

A decrease in the RDAI or in the respiratory rate during the study period is recorded as a negative RACS, meaning an improvement.

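### The SAP plans no by-child listing of vital signs or respiratory assessments, and its tables cannot in general show how many children worsened around a dose

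*SAP*

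**What the plan says.** Three parts of the SAP bear on this.

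- **General rule (SAP 4.2).** "All original and derived parameters as well as population characteristics will be listed and described using summary statistics". On extra measurements: "Repeated and unscheduled measurements will not be used for statistical analysis or summary tables", with narrow exceptions (a repeat made for technical reasons or because a value was unreliable, or a repeat before the first dose that serves as baseline). Then: "All listings will include repeated and unscheduled measurements".
- **Respiratory and vital-sign tables (SAP 6.7, mock Tables 14.3.3.1 to 14.3.4.2).** The categorical signs are counted: "respiratory muscle retractions (supraclavicular, intercostal, subcostal), daytime coughing and night-time coughing) will be tabulated by treatment group and time point". The mock of Table 14.3.4.2 has n (%) per category and time point, with no change or shift. Heart rate and SpO2 (Table 14.3.3.1) and respiratory rate (Table 14.3.4.1) get values and changes from baseline. SAP 4.3 fixes that reference: "The Baseline value is defined as the value observed at the last timepoint before first study drug administration".
- **Listings (SAP 14 and 15.2).** No entry covers serial vital signs or RDA findings. Listing 16.2.1.3 shows heart rate and SpO2 at baseline only.

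**The concern.** Protocol 1.3.3 names bronchoconstriction after inhalation as a potential risk to be closely monitored. It reports that 10 of 24 adults with hyperresponsive airways (42%) had a mild to moderate episode. It also says that the first-in-infant study gave salbutamol before every dose, which this trial does not require. SAP 6 says the safety evaluation takes the respiratory distress assessment into account.

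The natural question for a later reader is whether a given child's breathing worsened after a given inhalation. That needs either the child's own values in time order or a within-child comparison with the check before the same dose. The listing promised in SAP 4.2 would supply the first, but it is not in the index. The tables supply the second only for the continuous signs at dose 1. The data would have been collected around the dose and then reported in a form that hides most individual changes.

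**Working it through.** The SAP states no figure on this point, so the counts below are taken from its index, mocks and table shells.

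1. **Listings.** Index, SAP 14.1 to 14.8: 6 + 4 + 1 + 3 + 1 + 1 + 1 + 1 = 18. Mocks, SAP 15.2, Listings 16.2.1.x to 16.2.8.x: 6 + 4 + 1 + 3 + 1 + 1 + 1 + 1 = 18. Vital-sign or RDA listings: 0 in each. The index repeats two listing numbers, but the mocks are numbered without repeats and match it in content, so a numbering slip does not explain the absence.

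2. **Tables.** SAP 13 has 9 + 7 + 2 + 2 + 2 + 1 = 23 tables, and 4 of them cover vital signs or RDA. None compares wheeze, crackles or retractions within a child around any dose. None compares SpO2, heart rate or respiratory rate within a child around dose 2 or 3. At dose 1 the change from baseline is a proper before-and-after contrast, printed with minimum and maximum.

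3. **Unscheduled values.** SAP 4.2 keeps most of them out of tables and sends them to listings. With no such listing, most unscheduled respiratory values reach no indexed output. One point is unclear: SAP 3.3.1 counts lung auscultation as part of the physical examination, while SAP 6.6 leaves it out. Listing 16.2.5.1 may therefore show abnormal auscultation findings. Retractions, respiratory rate, heart rate and SpO2 would still be unlisted.

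4. **Categorical signs.** With n children, a affected before a dose and b after it, the number newly affected lies between max(0, b − a) and min(b, n − a). Take n = 12 (the planned active group in cohort 1) and assumed counts:

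| Before (a) | After (b) | Lower bound | Upper bound |
|---|---|---|---|
| 6 | 6 | max(0, 0) = 0 | min(6, 6) = 6 |
| 4 | 4 | max(0, 0) = 0 | min(4, 8) = 4 |
| 9 | 6 | max(0, −3) = 0 | min(6, 3) = 3 |
| 4 | 7 | max(0, 3) = 3 | min(7, 8) = 7 |

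The last row shows that a net rise does reveal some worsening. Stable or falling counts leave the number open.

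5. **Continuous signs on Days 2 and 3.** Invented SpO2 values for 12 children:
 - Baseline: 92, 92, 93, 93, 94, 94, 95, 95, 93, 92, 94, 96 (sum 1123)
 - Day 2 pre-dose: 97, 92, 95, 94, 96, 95, 97, 96, 95, 94, 96, 97 (sum 1144)
 - 2 h, set A: 97, 92, 94, 94, 96, 95, 97, 97, 95, 94, 96, 97 (sum 1144)
 - 2 h, set B: set A with children 1 and 2 exchanged (both have baseline 92)

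 At 2 h both sets give mean 1144/12 = 95.33, SD 1.614, median 95.5, range 92 to 97. Both give change from baseline with mean (1144 − 1123)/12 = 1.75, SD 1.215, median 2.0, range 0 to 5. The table rows are identical. The largest same-day fall is 1 point in A (child 3, 95 to 94) and 5 points in B (child 1, 97 to 92). The mean same-day change is (1144 − 1144)/12 = 0 in both. So the group mean over a dose can be recovered by subtracting rows when the same children are measured, but the worst child cannot.

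**The case against.** The case on the other side is substantial.

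- Protocol 5.4 asks only for descriptive statistics on these variables and reserves listing for physical-examination findings. SAP 6.7 meets that. This stands: the inconsistency is inside the SAP, between 4.2 and the index. A reader might infer an undeclared departure because SAP 9 is silent, but SAP 9 records departures from protocol-planned analyses, and the protocol planned no such listing.
- The printed minimum and maximum would show any fall below the pre-dose group minimum. The SpO2 example hides a 5-point fall only because another child rises by 5. This also stands: the example shows what is possible, not what is likely.
- Events judged adverse are visible. Protocol 3.6.3.2 and 3.6.3.4 make clinically significant oximetry changes and undesirable auscultation changes adverse events, and the AE listings carry nebulization times. Apnea, ventilation, therapies and interrupted inhalations are listed too. What is lost is mainly change that the investigator did not judge adverse.
- Only cohort 1 was randomized, development in infants was halted, and 3 placebo children give little context. This limits the stakes. It does not make one listing burdensome.

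Two stronger readings are tempting. One is that dropping the RACS removed a safety measure. The protocol places the RACS under clinical activity. It "is the sum of the change in the RDAI score and a standardized score for the change in respiratory rate", a single total with no stated same-day reference, so it would not have shown each sign around each dose. The other is that the laboratory table is a precedent for same-day pairing. It presents "the shift in abnormality (L/N/H/L+H) at the worst post-baseline time point, including unscheduled measurements", but against the pre-first-dose baseline, so copying it would leave doses 2 and 3 unpaired.

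**Conclusion.** The concern holds in a limited form. SAP 4.2 promises a listing that neither the index nor the mocks contain (0 of 18). If the index is followed, scheduled by-child respiratory values and most unscheduled ones reach no output, subject to the ambiguity about Listing 16.2.5.1. The tables cannot in general identify how many children worsened around a dose: any dose for the categorical signs, doses 2 and 3 for the continuous ones. The size is one of visibility: for example, 0 to 6 possible new wheezers behind an unchanged count of 6 in 12.

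A reader might infer that a signal was missed or that children went unprotected. The documents do not support that. SAP 1 records an IDMC meeting after cohort 1, and the protocol plans unblinded safety review at that point. Nor do the tables show nothing, since dose 1 is paired for the continuous signs.

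Assumptions: the planned 12:3 split held in cohort 1, and pre-dose, 2 h and 5 h checks were made on all three dosing days. The Schedule of Assessments reads clearly for Day 1, but its Day 2 and 3 columns look misaligned in the text available to me. The daytime-coughing row shows the Day 1 pattern throughout. The missing listing does not depend on the second assumption.

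**What to change.** **Main change.** Add one by-child listing of respiratory assessments and vital signs in time order, including unscheduled values. It should show wheeze, lung fields, crackles, retractions, respiratory rate, heart rate, SpO2 and oxygen delivered, with that day's nebulization start and end and any inhaled β2-agonist. This also reconciles SAP 4.2 with the index.

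**Descriptive supplement, on days with a same-day pre-dose value.**
- In Table 14.3.4.2, add per dosing day and arm the number of children whose wheeze or retraction category is worse at 2 h or 5 h than at that day's pre-dose check.
- In Tables 14.3.3.1 and 14.3.4.1, add the same-day change in SpO2, heart rate and respiratory rate on Days 2 and 3. Read SpO2 alongside oxygen delivered, because a change in oxygen can mask or mimic a change in the child.

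**Cost.** One listing and a few table rows for 15 children, at most 15 × 3 = 45 dosing days, with no new data. The output grows slightly. The 3 placebo children give little help in separating drug effect from the fluctuation of RSV illness, and a 2 h check can miss a brief reaction, so the added rows should stay descriptive.
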